6.1 Quantitative data analysis

Statistical analyses will be conducted using IBM SPSS Statistics 27. Participant characteristics will be described as medians (quartile intervals) for continuous variables and numbers (percentages) for categorical variables. Group differences in emotional granularity, emotional coping, and resilience will be examined using one-way ANOVAs and independent samples t-tests. Pearson's bivariate correlations will assess associations among emotional granularity, emotional coping, and resilience. Confirmatory factor analysis (CFA) will be performed using IBM SPSS Amos 27.0 to validate the measurement models, with acceptable model fit indices defined as $\chi^2/df \leq 3$, GFI, AGFI, CFI > 0.90, and RMSEA < 0.06 (Awad et al., 2022). A simple

mediation model will test whether emotional regulation mediates the relationship between emotional granularity and resilience using bootstrapping (5,000 resamples) and bias-corrected confidence intervals (Igartua & Hayes, 2021). Missing data will be handled using multiple imputation, and two-sided $p < 0.05$ will be considered statistically significant.

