Emotional granularity, also referred to as emotional differentiation or emotional complexity will be evaluated by RDEES. It was developed by American scholars Kang and Shaver in 2004 (Kang & Shaver, 2004). The original English version comprises 14 items across two subscales: Range and Differentiation. In 2013, Chinese researchers deleted 3 items from the original scale after translation and cultural adjustment, and finally obtained the Chinese version of the RDESS, which consists of 11 items, including the range of emotional experience and emotional experience differentiation dimensions, with a Cronbach's alpha coefficient of 0.82 (Wang H. et al., 2015).

The Chinese Version of Difficulties in Emotion Regulation Scale (DERS)

The version of the scale was developed in 2004 with 36 items to assess multidimensional challenges in emotion regulation, including nonacceptance of emotions, difficulties engaging in goal-directed behavior, impulse control issues, lack of emotional awareness, limited access to regulation strategies, and lack of emotional clarity (Gratz & Roemer, 2004). The English version has Cronbach's α of 0.93 and test-retest reliability (ICC = 0.88) over four to eight weeks.

Then the scale translated by Wang et al. in 2007 (Wang L., 2007), The Chinese version has Cronbach's α of 0.87, and test-retest reliability (ICC = 0.87).

The Chinese version of 10-item Connor-Davidson Resilience Scale (CDRS)

The original version of the scale is a self-administered questionnaire with one single dimension(Campbell-Sills et al., 2006), which originated from the original 25-item one (Connor et al., 2003). It has 10 items with five response options (0 = never; 4 = almost always). The final score of the questionnaire is the sum of the responses of each item (range 0 - 40), where higher scores indicate higher resilience capacity. It was translated into Chinese in 2017 (Ye et al., 2017). The Chinese version of CD-RISC-10 retains its single dimension in the original English version. Cronbach's α for the entire scale was 0.88, and the test-retest was 0.73.

5. Data collection for qualitative phase

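### GFI and AGFI above 0.90 are practically out of reach for an item-level maximum-likelihood CFA of the 36-item DERS at 200 to 236 participants, even when its model is exactly true

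*Combined protocol and SAP*

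**What the plan says.** Section 6.1 (Quantitative data analysis) plans a confirmatory factor analysis in Amos 27.0 "to validate the measurement models, with acceptable model fit indices defined as" chi-square/df of at most 3 and "GFI, AGFI, CFI > 0.90, and RMSEA < 0.06". One standard serves all scales. The section does not give the estimator, the level of the indicators, whether each scale has its own model, whether all five indices must be met, or what follows from misfit. No other section supplies these points.

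Section 4 describes the DERS as "developed in 2004 with 36 items to assess multidimensional challenges in emotion regulation" and lists six dimensions, the last two being "limited access to regulation strategies, and lack of emotional clarity". The Chinese RDEES is much shorter, "which consists of 11 items, including the range of emotional experience and emotional experience differentiation dimensions". The CD-RISC-10 has 10 items and one dimension.

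Section 3 (Participants) sets 200 participants for the mediation analysis, raised to at least 236 for 15% attrition. After the CFA, section 6.1 says that a simple "mediation model will test whether emotional regulation mediates the relationship between emotional granularity and resilience". It does not make that test conditional on the CFA.

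**The concern.** GFI and AGFI respond to more than misfit. With maximum likelihood they also fall as degrees of freedom grow relative to the sample size, because sampling error in many covariances counts against the model. A cut-off that a 10-item scale meets easily can therefore be unreachable for a 36-item scale in the same sample.

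The DERS measures the mediator. If the two indices count, its measurement model would be reported as fitting poorly whether or not it is correct, so the CFA could not do the job the plan gives it for this scale. Because the plan has no rule for misfit, it also leaves open whether items or error terms would be altered once the data are seen.

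**Working it through.** **1. Planned size.** 200/(1 − 0.15) = 235.3, rounded up to 236, which reproduces the plan. Simulated mediation power at n = 200 with the plan's a = 0.5 and b = 0.4 is about 99.8% to 99.95% (direct path assumed 0 or 0.2), consistent with the stated minimum of 80%. The CFA played no part in this sizing. The sample for the CFA is taken as 200 to 236.

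**2. Degrees of freedom for the DERS.** Assumed, because not stated: items as indicators, each loading on one of six correlated factors. Distinct variances and covariances: 36 × 37/2 = 666. Parameters: 36 loadings + 36 error variances + 15 factor correlations = 87. So df = 666 − 87 = 579, however the items are split across factors.

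**3. Expected indices under an exactly true model, maximum likelihood.** With p items, GFI ≈ p/(p + 2df/(n − 1)) and AGFI = 1 − [p(p + 1)/(2df)](1 − GFI).
- n = 200: GFI = 36/(36 + 1158/199) = 0.861; AGFI = 1 − (666/579)(0.139) = 0.840.
- n = 236: GFI = 36/(36 + 1158/235) = 0.880; AGFI = 1 − (666/579)(0.120) = 0.862.
- Expected GFI reaches 0.90 when 1158/(n − 1) = 4, that is n = 290.5. Expected AGFI reaches 0.90 at n = 338.8.
- A single-factor DERS that is exactly true (594 df) gives almost the same: 0.858/0.841 and 0.877/0.862.

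**4. Simulation.** Loadings and factor correlations were matched to the reported reliabilities: .5/.563 and .6/.34 for "The Chinese version has Cronbach's α of 0.87", and .7/.5 for "The English version has Cronbach's α of 0.93". Items were split 6/5/6/6/8/5. Responses were continuous, five-category symmetric, or five-category right-skewed (assumed cumulative proportions .45/.75/.90/.97). That makes 18 settings over the two sample sizes, with 1,000 runs each.

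| True six-factor model | n = 200 | n = 236 |
|---|---|---|
| Mean GFI | 0.844–0.861 | 0.865–0.880 |
| Mean AGFI | 0.820–0.840 | 0.844–0.862 |
| GFI > 0.90 | 0 of 9,000 | 4 of 9,000 |
| AGFI > 0.90 | 0 of 9,000 | 0 of 9,000 |

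A wrong one-factor model fitted to six-factor data passed neither index in 3,600 runs (mean GFI 0.60–0.83).

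**5. The other criteria in the same true-model runs.** RMSEA < 0.06 and chi-square/df ≤ 3 were met in all 18,000. CFI > 0.90 was met in 92% to 100% with continuous or symmetric items. With right-skewed items it was met, at n = 200 and 236, in 37% and 61% (loadings .5), 82% and 96% (.6), and 99% and 100% (.7). Since RMSEA < 0.06 means chi-square/df < 1 + 0.0036(n − 1), or 1.72 at n = 200 and 1.85 at n = 236, the limit of 3 adds nothing to it.

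**6. CFI and RMSEA both required.** In fresh runs this accepted the true DERS model in 16,615 of 18,000 (92%), the wrong one-factor model in 4 of 5,400, and a wrong three-factor model (factors merged in pairs) in 129 of 5,400. Both are needed: with loadings .5, RMSEA alone passed the one-factor model in 1,200 of 1,200 runs, whereas mean CFI there was 0.72–0.79 against 0.89–0.97 for the true model.

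**7. Other readings** (expected GFI/AGFI at n = 200 unless simulation is named).
- RDEES alone (43 df): 0.962/0.942. CD-RISC-10 alone (35 df): 0.966/0.947.
- All 57 items in one nine-factor model (1,503 df): 0.791/0.770.
- DERS by unweighted least squares (ULS): AGFI passed in 1,794 of 1,800 simulated runs.
- DERS with six subscale scores as indicators: 3,598 of 3,600 simulated runs passed. With 18 parcels: 0.937/0.911.

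**The case against.** The strongest reply is that the result needs three things the plan does not say: items as indicators, maximum likelihood, and GFI and AGFI both counting. Under ULS, subscale scores or parcels the cut-offs are attainable, and the plan cites a published study for them. This stands as a limit: the plan is not shown to fail on every reading. It does not remove the point, because item-level maximum likelihood is the natural reading, nothing in section 6.1 points elsewhere, and a citation does not make a cut-off attainable with 579 df at this sample size.

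The second reply is that no planned inference depends on the CFA. That stands in full. A reader might infer that the mediation estimate or its power is compromised; the documents do not support this, because the mediation model is specified separately and the study is sized on it alone. A reader might also infer that items will be dropped after a poor-fit verdict. No section says so, although none rules it out.

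Third, the remaining indices are imperfect: with strongly skewed items, maximum-likelihood CFI can miss 0.90 for a correct model. That is so, and the wording below carries a caution for it. CFI should still count, since RMSEA alone accepts a wrong model when loadings are low.

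**Conclusion.** The point holds in a limited form and is minor. With item-level maximum likelihood and all indices counting, a correct six-factor DERS model practically never exceeds 0.90 on GFI or AGFI at n = 200 to 236. The 0.90 line therefore cannot validate the scale or separate a right model from a wrong one. This rests mainly on p, df and n; the assumed loadings, correlations and response distributions move the means only slightly. The 236 is a minimum, but no larger sample is planned.

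Two stronger readings go too far. One is that all three scales fail: the RDEES and CD-RISC-10 are practically unaffected if each is fitted separately, and only a joint 57-item model would draw them in. The other is that GFI and AGFI carry no information: their values are lower for the wrong one-factor model, and it is the cut-off that does not discriminate. The harm is a false verdict of poor fit on the mediator's measure.

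**What to change.** In section 6.1, take GFI and AGFI out of the acceptance criteria and supply the missing specification, for example:

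> CFA will be fitted at item level by maximum likelihood, separately for each scale, with six correlated factors for the DERS. Fit is acceptable if CFI > 0.90 and RMSEA < 0.06; both are required and both values will be reported. GFI, AGFI and chi-square/df will be reported descriptively. With strongly skewed five-category items, maximum-likelihood CFI can fall below 0.90 for a correct model. A shortfall in CFI alone will be read with this in mind and will not lead to data-driven changes in the scale scores used in the mediation model.

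Both cut-offs are already in the plan. If the sponsor intends ULS or subscale scores as indicators, saying so is enough, and GFI and AGFI can stay.

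The cost is a few sentences, with no change to data collection or sample size. The downside is that two commonly reported indices no longer count as criteria.

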To be specific, young and middle-aged CRC patients (18 - 60 years) experienced higher occurrence rates for almost 50% of the symptoms due to their receipt of more intensive, shorter-cycle chemotherapy regimens, lower baseline functional status, and the emergence of unique chemotherapy-toxicity symptom clusters (Morse et al., 2024). Young and middle-aged cancer survivors (age < 60) with two or more comorbid conditions are more likely to have more and severe physical or emotional symptom (Jeon et al., 2019). In addition, compared to older patients, young and middle-aged patients are more likely to be exposed to complex social factors, such as financial stress and social isolation, following a cancer diagnosis. Specifically, the treatment of cancer will affect their work and thus cause severe economic toxicity (Alsakarneh et al., 2024; Ghazal et al., 2023); Social isolation is more common in young and middle-aged patients because cancer affects their careers and relationship (Fletcher et al., 2024; Khoo et al., 2022); For patients of childbearing age, the impact of cancer on their fertility is an even more specific negative factor in leading to a bad outcome (Baronas et al., 2024; Patel & Ahnen, 2018). Specifically for young and middle-aged CRC patients in China, studies have shown that they struggle to rebuild their social support networks and to access and screen

relevant health information, so that their health needs span the entire disease journey (Yajuan et al., 2024). In addition, CRC survivors frequently experience anxiety about treatment outcomes, future prognosis, and long-term survival, with emotional or psychological support and reassurance, information about managing illness and side effects, fear of cancer recurrence, and help with sexuality problems identified as their top unmet needs (Luo et al., 2024; Ng et al., 2019). Therefore, under such complex and numerous psychological and social challenges, resilience plays an important role in helping patients to cope well with the difficulties associated with cancer. Currently, few programs exist to enhance resilience in young and middle-aged colorectal cancer survivors after they finish primary treatment, even though they have distinct challenges. Developing tailored resilience-building interventions for this group will not only support their immediate well-being but also help them maintain better health as they age, thereby meeting their long-term medical and care needs.

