In summary, for young and middle-aged CRC patients, there are more key emotional and social factors challenges whether they arise from the disease, treatment outcomes, family responsibilities, career disruption or socialization. In this context, improving patient resilience can help them adapt to these stressors, maintain mental health, and recover from emotional setbacks. Although emotional methods have been available in existing research as effective and adaptive interventions to improve patient resilience (Casellas-Grau et al., 2014; Ding et al.,

2024; Polizzi & Lynn, 2021), so far there are no studies targeting on what and how effective of these emotional strategies adopted by the patients. Emotional granularity contributes to this process by enabling patients to recognize specific emotional experiences, which in turn enables them to more effectively apply targeted emotion regulation strategies. Therefore, we hypothesized that by increasing emotional granularity in young and middle-aged CRC patients, patients could use emotion regulation strategies more effectively in the face of the emotional complexity of the cancer journey, thereby improving patient resilience and promoting overall health as well as quality of survival.

Methods

1. Aim

To clarify the relationship between emotional granularity and resilience, explore young and middle-aged CRC patients' emotional challenges and investigate how resilient patients leverage emotional granularity to support adaptive emotion regulation strategies, as well as examine patients' perspectives on interventions development.

2. Study design

This study was designed as a sequential mixed-method study that first collects and analyses quantitative data and then qualitative data to explain or generalize quantitative data (Creswell & Clark, 2017). The study will include two-phases, including quantitative phase to explore the association among emotional granularity, emotional regulation and reliance in young and middle-aged CRC survivors, then a qualitative phase to further elucidate the findings from the quantitative phase and delve deeper into the emotional challenges faced by young and middle-aged CRC patients, as well as their perspectives on AI-integrated emotional interventions.

3. Participants

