The research design for the first quantitative phase is a cross-sectional, anonymous survey. young and middle-aged CRC patients will be recruited consecutively from Chinese medical institutions in Suzhou, Jiangsu Province. Potentially eligible participants will be identified from electronic medical records in accordance with the hospital's strict data security policies. The inclusion criteria are (1) young and middle-aged adult patients (age in the range of 18-60 years); (2) patients diagnosed with CRC; (3) patients have completed primary treatments (e.g., surgery, chemotherapy, and/or radiotherapy) without experiencing a recurrence of CRC; and (4) patients

able to use a smartphone and agree to participate in the study. The exclusion criteria are (1) patients who have not been informed of their cancer diagnosis due to family decision to withhold information; and (2) patients suffering from severe conditions that may affect participation or assessment, such as significant cognitive impairment, psychiatric disorders, or communication disorder. Before the survey, patients are required to sign an informed consent form. Regarding the sample size, Monte Carlo simulation for mediation analysis will be used (Donnelly et al., 2023; Fritz & MacKinnon, 2007). We will begin by specifying our population parameters based on the smallest effect size of interest (SESOI). In our mediation model, the following paths were defined: Path a is the effect of emotional granularity on emotional regulation. Path b is the effect of emotional coping on resilience (while controlling for emotional granularity). Path c is the direct effect of emotional granularity on resilience after accounting for the mediator (Figure 4). standardize example value of $a=0.5$, $b=0.4$ (Donnelly et al., 2023). 200 participants will reliably ensure at least 80% power. Moreover, considering a 15% attrition rate, the sample size should be 236 at least.

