Appendix

1. Emotion-resilience assessment questionnaire for young and middle-aged colorectal cancer patients (Chinese version)

第一部分：一般资料调查表

- *住院号（即患者唯一编号）:
- *年龄: _____ 岁
- *性别: 男 女
- *就业状态: 在职 学生 离/退休 待业 失业/无业
- *婚姻状态: 已婚 未婚 离异 丧偶
- *结直肠癌家族史: ①有 ②无
- *其他疾病: ①无 ②糖尿病 ③高血压 ④心脏病 ⑤其他_____
- *肿瘤位置: 结肠 直肠 结直肠 其他_____
- *结直肠癌 TNM 分期: T_N_M_
- *是否有造口: ①无
②有（结肠造口 回肠造口； 造口时间: _____年_____月_____日）
- *是否转移: _____（如是，请填写转移部位）
- *所接受过的治疗（可多选，请在横线上写出治疗开始和结束日期）:
手术_____ 化疗_____（请标注化疗方案）
放疗_____ 靶向_____ 免疫_____ 其他_____

13. *最后一次接受主要治疗的日期: ____年____月____日

14. *目前所遗留的肿瘤/造口相关并发症:

肿瘤/术后相关并发症	造口相关并发症	其他 (请详细填写)
 无	 无	
 低前切除综合征	 造口渗漏	
 肠道功能障碍	 腹旁疝	
 肠道梗阻	 周围皮肤并发症	
 吻合口狭窄	 造口脱垂	
 吻合口瘘	 造口狭窄	
 局部复发及相关并发症	 造口回缩	
 肿瘤复发/转移	 高排出造口	
	 造口梗阻	
	 感染与出血	

个人情况调查表

1. 家庭人均月收入 (元): <3000 3001~6000 6001~9000 >9000
2. 居住地: 城镇 农村
3. 付费方式: 全公费 城镇基本医疗保险 新型农村合作医疗
 商业医疗保险 其他社会保险 贫困救助 全自费
 其他 _____ (请具体填写)

第二部分 RDEES

请你仔细阅读每一项题目，在每一题后最符合自己情况的数字上画圈 “○”

1 表示“这完全不是对我的描述”。5 表示“这是对我的精准描述”。

题目	符合程度				
	1	2	3	4	5
1. 我知晓特定情绪的不同差异	1	2	3	4	5
2. 我一生中已体验到各种各样的情绪	1	2	3	4	5
3. 每种情绪对我而言都有着特殊涵义	1	2	3	4	5
4. 我能领悟到类似情绪之间的细微差异 (如沮丧和抑郁; 生气和恼怒)	1	2	3	4	5
5. 我情感丰富	1	2	3	4	5
6. 我知道每种情绪都蕴含着完全不同的意义	1	2	3	4	5
7. 在日常生活中, 我并没有体会到纷繁复杂的情绪	1	2	3	4	5
8. 如果用颜色来形容不同的情绪, 我可以注意到每一种颜色 (情绪) 之间的细微差别	1	2	3	4	5
9. 我能够意识到自身各种情绪感受之间的细微差别	1	2	3	4	5
10. 我倾向于体验到各种不同的情绪感受	1	2	3	4	5
11. 我擅长区分那些意思紧密关联的情绪词间的细微差异	1	2	3	4	5

第三部分 DERS

指导语：下面的量表用于评估您的情绪调节，每个问题有 5 种不同答案可供选择，请根据您最近的实际情绪调节体验实际情况，选择相应的答案打勾 “√”。

	从不	偶尔	有时	经常	总是
1. 我明白我的感受					
2. 我会注意我的感受是怎样的					
3. 我有过情绪极为强烈和情绪失控的经历					
4. 我不清楚自己的感受是怎样的					
5. 我很难弄明白自己的感受					
6. 我会留意自己的感受					
7. 我能清楚地知道自己的感受是怎样的					
8. 我在意我感受到什么					
9. 我对于自己的感受如何感到困惑					
10. 当心烦意乱时，我能觉察我有这个情绪					
11. 当心烦意乱时，我为有这种情绪而生自己的气					
12. 当心烦意乱时，我为有这种情绪而感到尴尬难堪					
13. 当心烦意乱时，我难以把事情（任务）完成					
14. 当心烦意乱时，我会变得失控					
15. 当心烦意乱时，我相信我会一直处于这种状态很长时间					
16. 当心烦意乱时，我相信最后我会感到相当抑郁					
17. 当心烦意乱时，我相信我的感觉是有根据和重要的					
18. 当心烦意乱时，我难以专注在其他事上。					
19. 当心烦意乱时，我感到失控					
20. 当心烦意乱时，我仍然能把事情做完					
21. 当心烦意乱时，我为自己有这种感受而感到羞愧。					
22. 当心烦意乱时，我知道我能够找到方法让自己最后的感觉好一些					
23. 当心烦意乱时，我觉得好像自己是软弱的。					

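### The mediation model in section 6.1 names no covariates, so the indirect effect is open to confounding by factors that the survey form already records

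*Combined protocol and SAP*

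**What the plan says.** Section 6.1 plans one inferential model for the main question: a simple "mediation model will test whether emotional regulation mediates the relationship between emotional granularity and resilience using bootstrapping", with 5,000 resamples and bias-corrected intervals. It names no covariate, no rule for choosing covariates and no sensitivity analysis for confounding. The t-tests and ANOVAs in the same section compare groups one variable at a time and are not linked to the mediation model.

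The sample size text in section 3 defines the paths. For path b it says "Path b is the effect of emotional coping on resilience (while controlling for emotional granularity"; the direct path conditions only on the mediator. No other conditioning appears.

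The general information form in Appendix 1 collects several candidate common causes: age, sex, TNM stage, stoma, other diseases ("其他疾病: ①无 ②糖尿病 ③高血压 ④心脏病 ⑤其他") and the date of the last primary treatment ("最后一次接受主要治疗的日期"). The background says that cancer survivors under 60 "with two or more comorbid conditions are more likely to have more and severe physical or emotional symptom".

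The study design section describes the quantitative phase as exploring association. The hypothesis that closes the background is causal: "we hypothesized that by increasing emotional granularity in young and middle-aged CRC patients, patients could use emotion regulation strategies more effectively".

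**The concern.** Nothing is randomised, and all three constructs are measured in one survey. Any factor that worsens emotion regulation and also lowers resilience will appear in path b as if regulation were acting on resilience. More patients narrow the interval around the wrong value but do not remove the bias.

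The plan's own account of comorbidity and emotional symptoms makes at least one recorded item a plausible common cause. Eligibility narrows some differences: age is 18 to 60, primary treatment is complete without recurrence, and severe conditions are excluded, "such as significant cognitive impairment, psychiatric disorders, or communication disorder". Differences in stage, stoma, comorbidity, time since treatment and subclinical distress remain.

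At stake are the size of the indirect effect and the coverage of its interval. If the true path b is small or zero, the finding of mediation itself is also at stake. Because the hypothesis is worded causally, an unadjusted estimate is easily over-read.

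**Working it through.** **Inputs from the plan (section 3).** Standardised a = 0.5 and b = 0.4, so ab = 0.20; 200 evaluable patients; 15% attrition; 236 recruited.

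**The plan's own figures.** 200/0.85 = 235.3, rounded up to 236; conversely 236 × 0.85 = 200.6. At N = 200 and the stated paths, simulated power is 99.9% or more for direct effects from 0 to 0.3. The claim of at least 80% is therefore true with much to spare.

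**Assumptions.** One omitted factor U, independent of granularity X, has standardised effects rM on regulation M and rY on resilience Y. The direct effect is c = 0.2. The documents give no value for rM, rY or c, so a range of confounder strengths is shown.

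M = aX + rM·U + e; Y = cX + bM + rY·U + e

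Expected unadjusted path b = b + rM·rY/(1 − a²), with 1 − a² = 0.75.

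**Planned paths, true ab = 0.20.** Same sign means that rM·rY has the sign of b.

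| rM / rY | Shift in b | Expected ab, same / opposite sign | Coverage of 0.20 |
|---|---|---|---|
| 0.1 / 0.1 | 0.01/0.75 = 0.013 | 0.21 / 0.19 | 95% |
| 0.2 / 0.2 | 0.04/0.75 = 0.053 | 0.23 / 0.17 | 89-92% |
| 0.3 / 0.1 | 0.03/0.75 = 0.040 | 0.22 / 0.18 | 92% |
| 0.3 / 0.3 | 0.09/0.75 = 0.120 | 0.26 / 0.14 | 71-73% |

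With no confounder, coverage is 95%. Coverage comes from simulated bias-corrected bootstrap intervals (1,000 resamples, 1,500 to 2,000 replicates); simulation error is about one percentage point at the lowest values. Mediation is still detected in 94-100% of samples throughout.

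**True b = 0, a = 0.5.** Frequency of false mediation:

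| rM / rY | Joint significance | Bias-corrected bootstrap |
|---|---|---|
| none | 5% | 7% |
| 0.1 / 0.1 | 6% | not run |
| 0.3 / 0.1 | 8% | 9% |
| 0.2 / 0.2 | 10% | 11% |
| 0.3 / 0.3 | 32% | 36% |

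Hand check of the last row. The shift in b is 0.12. The residual variance of Y is 1 − 0.2² − 0.12² × 0.75 = 0.949. The standard error of b is √(0.949/(200 × 0.75)) = 0.080, so the test statistic is centred at 0.12/0.080 = 1.5. It exceeds 1.97 about 32% of the time. Adjusting for U brings the joint significance rate back to about 5%.

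**If the factor also affects granularity.** With the same effect g on all three variables and c = 0.2, expected ab is 0.211, 0.245 and 0.310 at g = 0.1, 0.2 and 0.3. That is 5%, 23% and 55% above 0.20, so the same-sign values in the first table are the milder case.

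**How much adjustment recovers.** Suppose covariates capture a share p of U's variance. The remaining shift in b is (1 − p)·rM·rY/(1 − a² − p·rM²). At 0.3/0.3, same sign, ab falls from 0.26 to 0.25, 0.24, 0.23 and 0.20 at p = 10%, 30%, 50% and 100%.

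**Tipping point, with U independent of granularity.** An estimated b is fully explained when rM·rY = b(1 − a²). For b = 0.4 this is 0.4 × 0.75 = 0.30, or 0.55 on each path. For b = 0.2 it is 0.15, or 0.39 on each path.

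**The case against.** A simple mediation model can mean one predictor, one mediator and one outcome, which does not rule out covariates, and the path diagram (Figure 4) is not available. On that reading the plan is silent rather than committed to an unadjusted model. This is fair, but no covariate is planned anywhere, and silence leaves the choice until after the data are seen.

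The confounder strengths are hypothetical. At 0.1 on each path there is no practical harm, and no document shows that any recorded item reaches 0.3. The background sentence on comorbidity concerns symptoms, not regulation or resilience, so it makes a common cause plausible without demonstrating one. Adjustment may also recover little: if the recorded items carry 10-30% of a strong factor, 0.26 moves only to 0.25 or 0.24, and no measure of anxiety or depression is listed. These points stand. They limit how serious the concern is, and they are why adjustment needs a sensitivity calculation beside it.

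The false-mediation figures depend on which path is null. With both a and b zero and effects of 0.3 on all three variables, the rate is 5.7%; the 32% applies when path a is real and path b is not.

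Finally, the stated aim is associational. That is so, but the hypothesis is not, and the interview guide says that the work will inform an AI-integrated intervention.

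**Conclusion.** The concern holds and should be fixed before analysis. Followed as written, the plan produces an unadjusted indirect effect although plausible common causes are on the form. At the planned paths the harm is to the size of the estimate and the coverage of its interval, not to detection. It ranges from negligible at 0.1 on each path to an expected 0.14 or 0.26 against a true 0.20, with coverage near 72%, at 0.3. If path b is truly zero while path a is real, false mediation can reach 32% (joint significance) or 36% (bias-corrected bootstrap). These sizes rest on assumed confounder strengths, a linear standardised model, c = 0.2 and N = 200. That the model as written has no covariates rests on the documents alone.

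**What to change.** In section 6.1, make the primary mediation model covariate-adjusted.

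- Name one set in advance, on subject-matter grounds and not from the univariable tests, and enter it in both the mediator and the outcome equation. An example is age, sex, time since last primary treatment, TNM stage, stoma, and any comorbidity (yes/no).
- Use items that are on the form. Section 4 lists education, but the form as reproduced in Appendix 1 does not show it.
- Comorbidity is yes/no because the other-diseases item is not marked as allowing several answers, whereas the treatments item is. If the form can still change, mark it so, and the group with two or more conditions can then be identified.
- Include household income only with a stated reason for placing it before emotion regulation, since the background says "the treatment of cancer will affect their work and thus cause severe economic toxicity".
- Report the unadjusted model alongside.
- Add a calculation of how strong an unmeasured mediator-outcome confounder must be to bring the indirect effect to zero.
- Describe the result as an adjusted indirect association, and state that adjustment does not settle the order of three variables measured at one time.

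The cost is SAP wording, about 8 model terms and one sensitivity calculation. At N = 200 with a = b = 0.23, simulated power is 80.7% with no irrelevant terms, 78.9% with 8 and 78.5% with 10. At a = 0.5 and b = 0.4 it is 99.9% in each case. No change to the sample size is needed.
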